## 6.3 Definitions related to study Endpoints

### Resolution of Persistent Lymphopenia

Subjects who complete or drop out of a cladribine clinical trial with a Grade 3 or Grade 4 lymphopenia as defined by the Common Terminology Criteria for Adverse Events (CTCAE) [8] will be defined as having ‘persistent lymphopenia’ and will be monitored until lymphopenia resolves. Resolution is the achievement of a CTCAE Grade 1 or Grade 0 lymphocyte count.

According to the CTCAE version 4.03 [8], lymphopenia grades are defined as follows:

- Grade 1: < lower limit of normal (LLN) to 800/mm^3 or < LLN to 0.8 × 10^9/L
- Grade 2: < 800–500/mm^3 or < 0.8–0.5 × 10^9/L
- Grade 3: < 500–200/mm^3 or < 0.5–0.2 × 10^9/L
- Grade 4: < 200/mm^3 or < 0.2 × 10^9/L

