#### **8.3.1.1 Information from registry enrollment interview**

At the registry enrollment interview, the following data will be collected from all subjects unless prohibited by country regulations:

- Identification/contact information of subject, next of kin/caregiver, and current treating physician(s).

In subjects who have a lagged interval period and whose medical record is not accessible, a specific questionnaire will address the following:

- Treatment exposure to immunosuppressant medications, including type of treatment and date started;
- Occurrence of SAEs including time and outcome;
- Occurrence of AEs in the ‘Blood and Lymphatic System Disorders’ and ‘Neoplasms Benign, Malignant, and Unspecified’ SOCs including time and outcome
- In subjects tagged as “lymphopenic subjects” ascertainment of performance of a blood test during the lagged data period, and categorization of lymphocyte counts as normal, abnormal or unknown, if available.

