#### **8.3.1.2 Information from medical health records review**

For subjects with lagged data period, Sponsor will review data from medical records and the PRP will enter the following data into the registry participant electronic case report form:

- Treatment exposure to immunosuppressant medications, including type of treatment, and date started;
- Occurrence of SAEs including time and outcome;
- Occurrence of a pregnancy in participant woman, including date of LMP, and outcome;
- In subjects tagged as “lymphopenic subjects” ascertainment of performance of a blood test during the lagged data period, and categorization of lymphocyte counts as normal, Grade 1 through Grade 4 or unknown, if available.

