8.2 Definition of Analysis Populations and Subgroups

The registry target population includes all subjects who participated in Sponsor oral cladribine Phase I to III clinical trials in MS associated with a protocol approved prior to the time of submission of the marketing application and completed (last patient, last visit) after November 2008. This corresponds to five clinical trials (protocol number/study name):

- 25643/CLARITY
- 26593/ONWARD
- 27820/CLARITY EXTENSION
- 27967/Pantoprazole DDI
- 28821/ORACLE MS

Subjects will be analyzed according to their actual exposure to oral cladribine. There will be no per-protocol analysis population excluding patients with protocol deviations.

Safety Analysis Population (SAF)

The Safety Analysis Population will consist of all subjects from studies CLARITY, CLARITY EXT, ORACLE MS and ONWARD who are enrolled in the PREMIERE registry as full participants.

Lymphocyte Analysis Population

The lymphocyte analysis population consists of all subjects from SAF with at least one absolute lymphocyte count (ALC) value in PREMIERE, with an associated ALC date after the end of clinical trial.

DDI Safety Set

The **DDI** Safety Set will include all subjects from the Pantoprazole DDI study who are enrolled in the PREMIERE registry as full participants. In this study, subjects received two single doses of 10 mg cladribine separated by a wash-out of at least 10 days and two 40 mg doses of pantoprazole on two consecutive days. Data from the DDI Safety Set will be presented in listings only.

9 General Specifications for Data Analyses

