The duration (in months) of the resolved episodes (out of the unresolved at end of clinical trial period) will be summarized. In addition, use of MS-DMDs prior to resolution will be presented.

Resolution of lymphopenia computed using CRF tick box

Reporting will be done for SAF. This is an exception, to include the largest possible information available.

The number of subjects with declared Grade 3 or 4 lymphopenia at end of clinical trial [CRF Tick box], will be summarized together with their outcome in PREMIERE. The outcome in PREMIERE will be computed from those with at least one grade 0/1 in PREMIERE or with a CRF "resolution date".

Presentation per treatment group and total will be done.

Resolution of lymphopenia based on observed ALC value versus CRF tick box

A 2-by-2 table of number of subjects with and without resolution of lymphopenia at the end of clinical trial based on ALC value versus CRF Tick box will be presented.

In addition, a listing will be generated for subjects with unresolved lymphopenia at the end of clinical trial according to ALC grade, but with the CRF Tick box = "Resolved". The following variables will be displayed: Subject ID, cumulative dose of cladribine, previous clinical trial, treatment group (see section 9.1), all ALC values in PREMIERE with grade and date and tick box for resolved with date of resolved if available.

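### Lag-period lymphocyte results are listed as categories without a test date or value, and the interview category *abnormal* mixes resolved with unresolved counts, so resolutions in the lag may be dated late

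*Protocol*

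**What the plan says.** Time to resolution of persistent lymphopenia is one of three primary endpoints (Protocol 6.1). Subjects who leave the trial at Grade 3 or 4 are tagged as lymphopenic (Protocol 8.3.1.3), and Protocol 6.3 sets the end of the episode: "Resolution is the achievement of a CTCAE Grade 1 or Grade 0 lymphocyte count".

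Two lists describe what is collected for the lag between trial end and registry enrolment.

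- **Interview (Protocol 8.3.1.1).** It applies to a restricted group: "In subjects who have a lagged interval period and whose medical record is not accessible, a specific questionnaire will address the following". For tagged subjects it asks whether a blood test was done and for "categorization of lymphocyte counts as normal, abnormal or unknown, if available".
- **Records review (Protocol 8.3.1.2).** It asks for "categorization of lymphocyte counts as normal, Grade 1 through Grade 4 or unknown, if available".

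Neither lymphocyte item names a test date or a numeric count. Other items in the same lists do carry timing: a start date for immunosuppressants and, for serious events, "Occurrence of SAEs including time and outcome".

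The SAP works from dated counts. Its Lymphocyte Analysis Population (8.2) requires an ALC value "with an associated ALC date after the end of clinical trial". In 15.1.4 an episode closes at the next normal or Grade 1 ALC, and the summary reported is "The duration (in months) of the resolved episodes". SAP 9.12 rules out imputation.

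**The concern.** The interview category does not line up with the endpoint. A subject at Grade 1 has resolved under Protocol 6.3 but must be entered as *abnormal*, alongside subjects at Grades 2 to 4 who have not.

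The second problem affects both routes. Elapsed time is the endpoint, yet the item that should mark the end of that time carries no date. A resolution in the lag that is held only as a category is invisible to the ALC-based analysis until a dated Grade 0/1 count appears. The reported duration then includes the rest of the lag and the wait for that count. Table 1 of the SAP replaces the life table with descriptive statistics, and no interval-censoring rule is stated, so a late date passes straight into the summary.

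**Working it through.** The plan gives no figure here to reproduce. The check has two parts.

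**1. Map each recorded category to the resolution rule.** Inputs: the grade definitions and resolution rule in Protocol 6.3, where the Grade 1 entry begins "Grade 1: < lower limit of normal (LLN) to 800/mm", and the two category lists.

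| ALC grade | Resolved (6.3)? | Interview entry | Records-review entry |
|---|---|---|---|
| 0 | yes | normal | normal |
| 1 | yes | abnormal | Grade 1 |
| 2 | no | abnormal | Grade 2 |
| 3 | no | abnormal | Grade 3 |
| 4 | no | abnormal | Grade 4 |

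On the records route every entry except *unknown* maps to one outcome. On the interview route *normal* means resolved and *abnormal* is ambiguous. The only resolved result whose status is lost is a Grade 1 reported at interview. Both routes lack the date.

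**2. Size of the dating error.** The lag length, the number affected and the timing of the first dated count are not in the documents, so these are assumptions:

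- resolution falls uniformly over a lag of L months;
- no date is captured in the lag;
- the first dated ALC comes w months after enrolment and is still Grade 0/1.

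Resolution at time t in the lag is recorded at L + w, so the overstatement is L + w − t. Its mean is L/2 + w and its maximum is L + w. Protocol 8.2 and 8.4 suggest reference values for w: interviews every 3 months for two years, capturing any count since the last contact, and blood counts at least yearly until resolution.

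| L (months) | w = 0: mean / max | w = 3: mean / max | w = 12: mean / max |
|---|---|---|---|
| 3 | 1.5 / 3 | 4.5 / 6 | 13.5 / 15 |
| 12 | 6 / 12 | 9 / 15 | 18 / 24 |
| 24 | 12 / 24 | 15 / 27 | 24 / 36 |

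For example, with L = 12 and w = 3 the mean is 12/2 + 3 = 9 months. The SAP starts an episode at its first Grade 3 or worse count after baseline, which can be well before trial end. The delay is added to that whole duration, so it is an absolute number of months and not a ratio.

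**The case against.** Several points on the other side stand.

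- The records-review grades show the Grade 0/1 threshold in full, and *normal* at interview shows Grade 0. A reader might infer that lag data cannot show resolution at all. The mapping above contradicts that.
- The interview route is narrow. Protocol 8.1 calls the subjects without usable records limited in number and says medical confirmation will be sought where possible.
- A reader might infer that lag resolutions are generally missed. SAP 15.1.4 accepts any later Grade 0/1 count, and in its tick-box analysis also a CRF resolution date. A miss in the ALC-based analysis needs the absence of any later dated Grade 0/1 count. The tick-box analysis, however, has no stated duration summary.
- The SAP does not exclude lag counts. Registry Day 1 is the day after trial end (9.6), and the ALC registry baseline takes the first dated value from then on. The gap lies in what the protocol lists for collection.
- The lag questionnaire and e-CRF are not in the documents. Protocol 8.1 says records are reviewed for lymphocyte counts, which suggests fuller capture than 8.3.1.2 lists. Lag adverse events are also to carry time and outcome, and Protocol 5.7 and 8.5.1.5 count unresolved lymphopenia among ongoing SAEs, so a date may exist there. SAP 15.1.4 does not say that such dates feed the ALC-based duration.

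A delay of 36 months appears only at the extreme of the assumed ranges, L = 24 with w = 12. It should not be quoted as expected. Nor is every consequence in one direction: late dating lengthens durations, but a subject with no dated post-trial count leaves the Lymphocyte Analysis Population, and the effect of that exclusion is not known.

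**Conclusion.** The point holds in a limited form. *Abnormal* at interview cannot separate Grade 1 from Grades 2 to 4, and neither lag list includes the test date or the ALC value. The main effect is late dating in the duration summary, with missed resolution a secondary risk. Under the uniform assumption and a lag of 3 to 24 months, mean overstatement per affected subject is 1.5 to 12 months at w = 0 and 4.5 to 15 months at w = 3. The effect on the summary as a whole cannot be stated, because the share of tagged subjects who resolved in the lag is not given. If the actual forms did capture dates and values, what remains is a mismatch between the protocol lists and the forms.

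**What to change.** **Protocol.** In 8.3.1.2, and in 8.3.1.1 where a result can be obtained, list the date of each lag test and the ALC value with its unit, or Grade 0 to 4 with the date if no value exists. At interview, *abnormal* should not be read as unresolved; without a grade, lag status is unknown.

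**SAP 15.1.4.** No change is needed to admit dated lag values. Add two things:

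- the number of category-only or undated lag results, by route;
- for those known to be Grade 0/1, resolution time shown as an interval from the last unresolved dated count to registry enrolment, with the duration summary reported at both ends.

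In the L = 12, w = 3 example, with the last unresolved dated count at trial end, post-trial time to resolution would be shown as 0 to 12 months where it would otherwise be recorded as 15.

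**Cost.** A few more fields in a review that sites already carry out, and some durations shown as ranges. A subject without records may be unable to supply a value or date, so the interview gain may be small. SAP Section 6 gives the last visit as 25 October 2018. For data already collected, the change is therefore the SAP wording, after checking which lag dates and values the e-CRF holds.

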#### **8.3.1.2 Information from medical health records review**

For subjects with lagged data period, Sponsor will review data from medical records and the PRP will enter the following data into the registry participant electronic case report form:

- Treatment exposure to immunosuppressant medications, including type of treatment, and date started;
- Occurrence of SAEs including time and outcome;
- Occurrence of a pregnancy in participant woman, including date of LMP, and outcome;
- In subjects tagged as “lymphopenic subjects” ascertainment of performance of a blood test during the lagged data period, and categorization of lymphocyte counts as normal, Grade 1 through Grade 4 or unknown, if available.

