## 6 Study Endpoints

### 6.1 Primary Endpoints

- Cumulative incidence of SADR, including malignancies and serious infections
- Time to resolution of lymphopenia, among registry participants with persistent lymphopenia

- Cumulative incidence of all AEs in the “Blood and Lymphatic System Disorders” System Organ Class (SOC) and in the “Neoplasms Benign, Malignant, and Unspecified” SOC

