### Medical Records

For subjects who withdrew or completed the clinical trial before the registry was established (but who are still followed at the site), health records will be retrospectively reviewed to ascertain SADRs, pregnancies, and lymphocyte counts, as well as exposure to immunosuppressants occurring during the lagged data period.

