15.3 Adverse Events

Reporting will be done for SAF.

Adverse events are events that are reported with a start date on or after the end of clinical trial + 1 day [Registry Day 1].

AEs collected in PREMIERE either from AEs CRF Pages (AE dataset) or New Diagnoses CRF Pages (CE dataset) will be included.

Seriousness is not collected for events in the New Diagnoses CRF Pages. Seriousness will not be imputed and therefore these diagnoses will not be included in serious or non-serious AE tables.

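### The lag-interval record review has no line for non-serious AEs in the two primary-endpoint SOCs, although the questionnaire used when records are not accessible does

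*Protocol*

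**What the plan says.** The third primary endpoint covers every AE in the two SOCs, serious or not: Protocol 6.1 begins it "Cumulative incidence of all AEs in the" and names the Blood and Lymphatic and the Neoplasm SOCs.

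Lag data come from one of two sources.

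- **Questionnaire (Protocol 8.3.1.1).** "In subjects who have a lagged interval period and whose medical record is not accessible, a specific questionnaire will address the following". Its items include SAEs and, on a separate line, "Occurrence of AEs in the ‘Blood and Lymphatic System Disorders’ and ‘Neoplasms Benign, Malignant, and Unspecified’ SOCs including time and outcome". For tagged lymphopenic subjects it asks for "categorization of lymphocyte counts as normal, abnormal or unknown, if available".
- **Record review (Protocol 8.3.1.2).** "For subjects with lagged data period, Sponsor will review data from medical records and the PRP will enter the following data". The items are immunosuppressants, "Occurrence of SAEs including time and outcome", pregnancy and, for tagged subjects, lymphocyte counts as normal, Grade 1 to 4 or unknown. Section 8.1 (Medical Records) describes the same review: "health records will be retrospectively reviewed to ascertain SADRs, pregnancies, and lymphocyte counts", plus immunosuppressants. Neither text mentions AEs in the two SOCs.

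The SAP starts its safety analysis period the day after trial end (9.2), defines Registry Day 1 as that date and not as the enrolment date (9.6), and states in 15.3: "Adverse events are events that are reported with a start date on or after the end of clinical trial + 1 day". Sections 15.1.2 and 15.1.3 select any preferred term in each SOC. Patient-years run from trial end (10.1, 15.1.1).

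**The concern.** Two subjects with the same non-serious lag event, such as a mild cytopenia or a benign neoplasm, are treated differently. The one without an accessible record is asked about it. The one whose record is open in front of the site has no field for it. The fuller source therefore has the shorter event list.

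At stake is a crude incidence that is a primary result. The lag adds patient-time for everyone, but non-serious events from it are sought only in the questionnaire group. The bias is towards too low an incidence in record-reviewed subjects, and nothing in the SAP would reveal it: Table 1 of Section 7 does not mention it and 9.12 imputes nothing.

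**Working it through.** **Step 1: compare the lists with the endpoint.**

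| Item in the lag | Questionnaire, 8.3.1.1 | Record review, 8.3.1.2 | Record review, 8.1 | Needed for |
|---|---|---|---|---|
| Serious events | SAEs | SAEs | SADRs | Endpoints 1 and 3 |
| All AEs in the two SOCs | yes | no | no | Endpoint 3 |
| Pregnancy | no | yes | yes | Secondary endpoint |
| Lymphocyte count | normal / abnormal / unknown | normal / Grade 1–4 / unknown | counts | Endpoint 2 |
| Date of that count | not listed | not listed | not listed | Endpoint 2 |

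The pregnancy row differs in the other direction, which suggests that the lists were never harmonised. Protocol 8.1 (Subject Interviews) calls the group without records limited in number, so the shorter list probably governs most lag subjects.

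**Step 2: look for another provision that closes the gap.** Protocol 8.5.1.5 has a rule for lag events not reported in the prior trial, but it covers SAEs only. Section 8.5.2 asks for all two-SOC AEs over the study, while the reporting period in 8.5.1.5, defined for SAEs, opens at consent. Appendix I lists a lag questionnaire where applicable and does not widen who receives it.

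**Step 3: check that the lag is counted.** SAP 9.2, 9.6 and 15.3 start the count at trial end + 1 day, and 15.1.2 and 15.1.3 do not restrict to serious events. The protocol's own cumulative period (9.2.2) also spans the lag, so the gap does not come from the SAP's change of window.

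**Step 4: illustrate the size.** The plan states no figure to reproduce, and gives no lag length, number of lag subjects, record split or event rate. All values below are assumed, except the 1161 full participants (SAP Section 7, Table 1). That total includes any pantoprazole-interaction subjects, whom the Safety Analysis Population excludes.

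Let p be the true incidence of non-serious two-SOC AEs over the window and f the lag's share of the window. Assume a constant event rate and no such event captured in the lag. Observed incidence in affected subjects is then

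O = 1 − (1 − p)^(1 − f).

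With p = 5%:

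- f = 0.10: 1 − 0.95^0.90 = 4.51%
- f = 0.25: 1 − 0.95^0.75 = 3.77%
- f = 0.40: 1 − 0.95^0.60 = 3.03%

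The relative losses are 9.8%, 24.5% and 39.4%. For p = 2% they are 9.9%, 24.8% and 39.8%, and for p = 10% they are 9.5%, 24.0% and 38.7%. The loss is close to f itself, so the formula largely returns what was assumed.

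If a share a of the cohort is affected, the number of subjects with an event missed is 1161 × a × (p − O):

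- a = 0.25, f = 0.10: 1161 × 0.25 × (0.0500 − 0.0451) ≈ 1.4; overall incidence 4.9%
- a = 0.75, f = 0.40: 1161 × 0.75 × (0.0500 − 0.0303) ≈ 17.1; overall incidence 3.5%

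**The case against.** The strongest reply is that the gap is narrow and its effect unproven.

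- **Much is captured as serious.** Protocol 8.5.1.3 makes every malignancy, including non-melanoma skin cancer, reportable as an SAE, and gives blood dyscrasias without hospitalisation as an example of an important medical event. Sections 5.7 and 8.5.1.5 treat persistent Grade 3 or 4 lymphopenia as an SAE. This stands. It confines the point to blood and lymphatic AEs judged non-serious and to non-serious benign or unspecified neoplasms.
- **There is a second data source.** SAP 15.3 also counts the New Diagnoses pages. A reader might infer that a non-serious lag event in the record can never reach the analysis, and the documents do not support that. They do not describe those pages as a planned search of lag records for these SOCs either.
- **Earlier forms are not shown.** The registry began in 2009 (Protocol 10.1.2), while prospective two-SOC collection starts on local approval of amendment 1, dated July 2012 (Section 5). SAP Section 6 describes the amendment as a simplification. What was omitted for earlier enrollees cannot be read from the current 8.3.1.2. This limits what can be said about data already collected, but the current lists still differ.
- **Some subjects may have no lag.** Protocol 5.2.2 has the trial physician enrol subjects whose trial ended after registry initiation. This affects the size, not the mismatch.

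Three other stronger readings should be resisted. First, a reader might conclude that lymphopenia resolution in the lag cannot be graded or dated, and so is dated late by up to the whole lag. Record review does grade the counts, and SAP 15.1.4 uses a CRF resolution date and cross-tabulates count-based against tick-box resolution. Second, the lag's share of the window might be taken as the share of events lost, but it rests on assumed durations. Third, the lag might be called the time when haematological effects are most likely. Protocol Section 3 gives trial nadirs at Weeks 16 and 55 and nothing that locates a peak in the lag.

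**Conclusion.** The point holds as a defect in the written plan. In record-reviewed subjects, non-serious blood or lymphatic AEs and non-serious benign or unspecified neoplasms in the lag are not systematically collected, while the SAP counts both the events and the patient-time. Ascertainment of the third primary endpoint therefore depends on the lag source, and the expected direction is under-counting where records were reviewed.

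The size is unknown. The range of about 1 to 17 subjects is an illustration on assumed values. It also supposes complete collection after enrolment, which the amendment date makes doubtful for early enrollees in both groups.

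A smaller, related point concerns the second primary endpoint. The questionnaire's single abnormal category merges Grade 1, which counts as resolved under Protocol 6.3, with Grades 2 to 4, which do not. Neither list asks for the date of the lag count. An undated category cannot enter the count-based analysis, since the Lymphocyte Analysis Population (SAP 8.2) needs a dated value. The CRF resolution date may already cover some of these subjects.

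**What to change.** - **Protocol.** Add the questionnaire's two-SOC line, with time and outcome, to 8.3.1.2 and to the record review in 8.1, so that both sources use one event list. This costs one line on a form for records already being read for SAEs.
- **Subjects already enrolled.** Do not re-open records. The SAP gives the last visit as 25 October 2018 and the protocol plans about 234 sites, so a repeat review would be out of proportion. Instead, present the results of SAP 15.1.2 and 15.1.3 by lag source (no lag, record review, questionnaire). This costs one descriptive split and needs only an indicator of source. The groups may differ in other ways, so the split shows whether ascertainment looks uneven but does not correct it.
- **Lymphocyte counts.** In both lists, record a grade or value with its date where available. The cost is one or two fields for tagged subjects.
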